### 6.3.1 Follow-up procedure for withdrawn patients

All withdrawn patients should be recorded by the Investigator in the appropriate pages of the CRF when considered as confirmed. If possible, the patients should be assessed using the procedure planned for the end of study visit.

If an event causing dropout corresponds to the definition of a Serious AE/ADR, the investigator carries out the pharmacovigilance procedure described.

For patients considered lost to follow-up, the CRF must be filled in up to the last visit performed. The Investigator should make every effort to re-contact and to identify the reason why the patient failed to attend the visit and to determine his/her health status.

In case of death autopsy will be strongly encouraged for evaluation of pathology and presence of transplanted cells.

#### 6.3.1.1 Natural study termination

At the end of total follow-up.

#### 6.3.1.2 Premature Termination or Suspension of study

This study may be temporarily suspended or prematurely terminated if there is sufficient reasonable cause or if any of the stopping criteria described in this protocol occurs. Circumstances that may warrant termination or suspension include, but are not limited to:

- determination of unexpected, significant, or unacceptable risk to participants;
- demonstration of efficacy that would warrant stopping;
- insufficient compliance to protocol requirements;
- data that are not sufficiently complete and/or evaluable;
- determination of futility;
- reconsideration of the risk/benefit ratio.

Written notification, documenting the reason for study suspension or termination, will be provided by the suspending or terminating party to <investigator, funding agency, the sponsor and regulatory authorities>.

If the study is prematurely terminated or suspended, the PI will promptly inform the Institutional Review Boards (IRBs) and/or Independent Ethics Committees (IECs), will provide the reason(s) for the termination or suspension and will instruct additional procedures to be followed in order to ensure that adequate consideration is given to the protection of the patient's interests.

For patients who have received the ATIMP, a long term safety follow-up it is required by law. Study may resume once concerns about safety, protocol compliance, data quality are addressed and satisfy the sponsor, IRB and/or CA.

## 7 Treatment Plan

### 7.1 Experimental Treatment/Drug

The protocol will consist of a total of four treatment cohorts (TC), labeled from A to D, each of which receiving a single escalating dose of allogeneic hNPCs injected intrathecally, as it follows:

- TC-A:  $0.7 \times 10^6 \pm 10\%$  cells/kg of body weight;
- TC-B:  $1.4 \times 10^6 \pm 10\%$  cells/kg of body weight;
- TC-C:  $2.8 \times 10^6 \pm 10\%$  cells/kg of body weight;
- TC-D:  $5.7 \times 10^6 \pm 10\%$  cells/kg of body weight.

The intrathecal injection of hNPCs will be performed in a hospitalized setting.

The patients will be left in Trendelenburg position for about 30 minutes and monitored for at least 24 hours. All patients will receive normal saline solution (500 cc).

Body temperature, blood pressure, heart rate and oxygen saturation will be measured at baseline and after 15, 60, 180 minutes and then before discharge. Any toxicity will be treated at the discretion of the attending neurologist.

All patients will receive an i.v. dose of **methylprednisolone** (125 mg) immediately prior to lumbar puncture.

The injections of cells will be performed with lumbar puncture in lateral decubitus position removing about 10 cc of CSF that will be used for chemical-physical, infectivological analysis and OBs/ BBB analysis. 2 CSF ml will be stored for further research analysis. CSF will be replaced with the 10 cc of suspension solution containing hNPCs (at 2 ml/min injection rate). The injection of stem cell will be performed in about 5 minutes. In case of traumatic lumbar puncture with haematic CSF, the injection of hNPCs will not be performed. A second attempt will be performed after  $15 \pm 3$  days.

### 7.2 Immunosuppression:

Human NPCs have been shown to be relatively low immunogenic (e.g., no expression of MHC-I molecules and low levels of MHC-II molecules). However, as they are human in origin their transplantation will be handled like other organ transplant in order to prevent the unexpected rejection (if any) of transplanted hNPCs and we have planned to put our patients on long term immune suppression. The immunosuppression will be applied in agreement with previous studies with hNPCs in Amyotrophic Lateral Sclerosis and in children affected by neuronal ceroid lipofuscinosis and and Pelizaeus-Merzbacher disease. In all these studies the patients a long lasting immunosuppression was applied in order to guarantee the engraftment of stem cell. Data deriving by these studies confirmed that immunosuppression was well tolerated by the majority of patients and no opportunistic infections were reported till now.

According to our hematologist guidelines the patients will receive and oral prednisolone as explained below.

Tacrolimus (FK506) is a macrolide lactone with potent immunosuppressive activity 100 times that of cyclosporine by weight. The molecular mechanism of action is mediated via an inhibition of the phosphorylase activity of calcineurin by drug-immunophilin complex, resulting in the inhibition of IL-2 gene expression.

There are many studies now showing significant efficacy of tacrolimus in GVHD prevention in both allogeneic HSCT.

**FK506:** The initial oral dose of tacrolimus will be 0.05 mg/kg twice daily from day-7. Tacrolimus, if tolerated, will be given and gradually tapered till week 96.

A pharmacological surveillance of FK506 through drug level for consequent dose adjustment will be performed.

In order to maintain a target of 5-10 ng/ml, whole blood levels of tacrolimus will be obtained:

- two times a week until the therapeutic range was reached (first samples on day -4 and day -1);
- weekly till week 4 after hNPCs injection;
- at week 8, 12, 24, 36, 48 and then every 24 weeks till the end of follow-up.

Tacrolimus will be started day -7 before hNPCs injection as immunosuppressive medication to prevent the rejection of the cells, and it is expected that the patients will take the drug for the end of the follow-up.

Dose modifications of tacrolimus were dependent primarily on serum creatinine and the blood levels of tacrolimus. A dose reduction of at least 25% was mandatory for patients with a creatinine elevated to greater than 2.0 times baseline and at least a 50% reduction for patients with a creatinine greater than 3 times baseline.

Oral prednisone (deltacortene) 50 mg tapering of 5 mg every five days as follows dosage: 37,5 mg, 25mg, 12,5 mg and 5 mg.

Any or all the immunosuppressive agents may be reduced or stop at the discretion of the investigator if it is suspected or determined that the immunosuppressive agent is the cause of toxicity and if symptoms cannot be managed adequately with symptomatic treatment.

Anti-infective prophylaxis will be administered for the duration of FK506/tacrolimus therapy with acyclovir (1 tablet-800 mg twice daily), and co-trimoxazole (1 tablet-800 mg/160 mg, three times/week. Folic acid (1 tablet of 5 mg) will be administered with co-trimoxazole, as supportive therapy to reduce co-trimoxazole myelotoxicity three times a week.

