1: General Physical examination on Day 0 will be performed before hNPCs Injection and the day after before discharge. 2: Pulse rate, systolic and diastolic blood pressure, respiration rate and axillary temperature. 3: Vital signs (pulse rate, systolic and diastolic blood pressure, respiration rate and axillary temperature) will be obtained before hNPCs injection and then after 15', 60' and 3 hours after the end of injection. 4: Complete blood cell count; Extensive clinical laboratory evaluations: PCR, LDH, Total Protein, albumin, IgG, IgA, IgM, AST, ALT, GGT, ALP, Na+, K+, Ca++, urea, uric acid, alkaline phosphatase, Total Bilirubin, Direct Bilirubin, Glucose, creatinine, creatinine clearance, ferritin, Serum Iron, transferrin, transferrin saturation, PT, PTT, urin analysis. 5: complete blood cell count, blood chemistry and urin analysis: PCR, AST, ALT, GGT, Na+, K+, Ca++, Total Bilirubin, Direct Bilirubin, Glucose, creatinine, creatinine clearance, LDH, urin analysis; 6: Blood chemistry (note 5) will be performed at day -1 only if not performed within seven days. 7: infectivological panel at screening: HBs-Ag, HBs-Ab, HBe-Ag, HBe-IgG, HBe-IgM, HBV-DNA, HCV-Ab, HCV-RNA, HIV-Ab, VZV-IgG, VZV-IgM, HSV1-IgG, HSV1-IgM, EBV-IgG, EBV-IgM, EBV-DNA, CMV-IgG, CMV-IgM, CMV-DNA, Toxo-IgG, Toxo-IgM, HSV2-IgG, HSV2-IgM, Galactomannan detection, TPHA, Quantiferon. 8: infectivological panel during follow-up: CMVDNA, EBV-DNA Galactomannan detection. 9: explained in detail in the main test, overall 25 mLs heparinized blood+ 5 mLs serum. 10: tacrolimus: will be administered as explained in the text and monitored as explained in the specified chapter. 11: prophylactic treatment are explained in the specified chapter. 12: Oral prednisone (deltacortene) will be administered only from day -1 till week 4 as explained in the text. 13: CSF examination will be performed at the same time of hNPCs administration. 14: At week 12 we will perform a brain and total spinal cord MRI with gadolinium for safety reason heparinized blood+ 5 mLs serum. 15: The pregnancy test will be performed always by urine, except the control before inclusion that will be done by serum. Emo1 = Complete blood cell count

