**Infective Complication due to Immunosuppressive treatments**

To address the risk of opportunistic infections and organ toxicity due to combined steroid and tacrolimus treatment, periodic clinical, biochemical (full blood count, renal and liver function) drug level (FK506), immunological and virological monitoring (PCR for cytomegalovirus-CMV and Epstein virus-EBV) will be instituted at fixed intervals (see details in the specific chapter) and depending on patient's clinical and biochemical condition and previous findings, for the entire duration of the immunosuppressive treatment.

Pre-emptive CMV reactivation will be treated by standard treatment for immunosuppressed patients (i.e. ganciclovir or foscarnet). Immunosuppression reduction or discontinuation can be considered depending on severity.

EBV reactivation will be treated with immunosuppressive drug reduction or discontinuation and/or anti-CD20 (Rituximab) depending on the copy level and patient's clinical condition.

Recurrent episodes of CMV reactivation will be addressed with reduction of the immunosuppressive drug tacrolimus. Immunosuppression discontinuation will be considered depending on severity.

Bacterial infection will be treated according to standards. Repeated infections will be addressed by reduction or discontinuation of immunosuppression depending on site of infection, severity and patient's condition.

The safety profile related to concomitant medication will be assessed through general physical examination, neurological visit and through blood examination specifically hematology and chemistry parameters. At every visit signs and symptoms of possible infective events will be recorded.

For all the concomitant medication and procedure used in the protocol only AEs exceeding the grade 3 of severity according to the international definition of AEs will be reported (see also CTCAE).

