### **7.12 Prohibited Concomitant Therapy**

Concomitant treatment with any of the following is *not* allowed while receiving study treatment, unless as otherwise described in this protocol:

- Any non-study drug treatments directed toward the treatment of MS such as immunomodulatory treatments or chronic immunosuppressant therapy except tacrolimus
- Any investigational product, including investigational symptomatic therapies for MS and investigational therapies for non-MS indications

-Systemic steroid therapy including, but not limited to, oral corticosteroids (e.g., prednisone) or periodic (e.g., monthly) treatment with IV methylprednisolone, except for protocol-defined treatment of relapses as described above and course of oral prednisolone at the above mentioned dosage in the first 25 days after hNPCs injection.

Subjects who receive any of these restricted treatments may be required to permanently discontinue study treatment.

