### 8.3 Study Procedure and Study Flow-chart

#### 8.3.1 Enrolment phase

Is the process of informed consent signature (described in the ethical consideration chapter). Starting from the signature of the informed consent by the patient or patients' legal tutors, the subjects will be enrolled in the clinical trial. When the enrolment is confirmed the patient screening number will be assigned consecutively in increasing order starting with '001'. The list will be filed with the investigator's file. After the enrolment of a patient in the study, the investigator sends the enrolment module to the principle investigator by fax or email to clinical research monitor.

Those protocol phases are foreseen after signature of the informed consent:

- **Screening/baseline phase**, during which the conditions required by the clinical protocol for patients' inclusion/exclusion will be assessed (screened subject). The duration will be of three weeks (+/- 3 working days). At the end of the screening phase, the inclusion/exclusion criteria of the study will be evaluated (enclosed subject).
- **Pre-treatment phase**: carried from the end of the screening phase to the day before the start of treatment.
- **Treatment phase**: The intrathecally administration of hNPCs will be performed on day 0. Prophylactical treatment with Tacrolimus will be performed for 96 weeks starting from day -7 whereas oral corticosteroids will be administered for the first 4 weeks.
- **Follow-up phase**: 96 weeks after the experimental drug administration day 0.

At the end specify if the end of total follow-up or single patient follow-up.

At the end of the total follow-up, for all patients enrolled and treated in the study is planned a long term follow up, in accordance with the national applicable laws and the international guidelines.

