#### Day -1

- Neurological examination comprehensive of EDSS scale
- Vital signs
- AEs, SAEs record
- Relapse Assessment
- Concomitant medication revision
- Haematological blood examination: complete blood cell count, blood chemistry: will be performed if not performed within seven days
- Prednisone (Deltacortene) administration (50 mg)

At the end of all these assessment, patients will be assigned to one of the four different cohort of treatment (A-D) (see chapter Methods of assigning patients to treatment groups).

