### 8.3.5 Follow-up Phase

The follow-up phase will have a duration of 96 weeks. However the patients we'll be followed for the further 6 years at least.

Patients will attend control visits weekly for the first 4 weeks after hNPCs administration and then at 8 and 12 weeks. Starting from 12 weeks visits will be performed every 12 weeks. The procedures of each visit are described in details in the flow chart.

During the follow-up phase patients will receive tacrolimus, acyclovir, co-trimoxazole and folates for the entire follow-up (till week 96) and oral prednisone for 4 weeks.

The patient will undergo:

- Neurological visit with EDSS at week 4, 12, and then every scheduled visit
- T25FW, 9-HPT, SDMT at week 24, 48, 72, 96
- Haematological visit at week 4, 12, and then every scheduled visit
- General physical examination at every scheduled visit
- Record of vital signs at every scheduled visit
- AEs, SAEs record- Relapse Assessment at every scheduled visit
- Concomitant medication revision at every scheduled visit
- **Haematological blood tests comprehensive of:**

Complete blood count, extensive clinical laboratory evaluations will be performed at week 4, 12, 24, 48 and 96

Complete blood tests and biochemistry, urinalysis evaluation will be performed at week 2, 8, 36, 60, 72 and 84

Complete blood count evaluation will be performed at week 16, 20, 30, 42, 54, 66, 78 and 90

- Infectivological screening: CMV-DNA, EBV-DNA, Galactomannan detection will be performed at week 4, 12, 24, 48 and 96
- Immunological analysis: will be performed at week 4, 12, 24, 48 and 96
- Whole blood levels of tacrolimus will be obtained as reported in the specific section, in order to maintain a target of 5-10 ng/ml.
- CSF examination will be performed at week 12. During this visit the patient will be admitted to the hospital in the morning and will be discharged the day after (24 hours of observation after procedure). Complete chemico-physical evaluation, oligoclonal bands detection, CSF Cell evaluation, virological screening, ddPCR assays.
- Electrocardiogram, Chest Xray will be performed at visit week 48 e 96 and abdominal ultrasound only at visit 96
- Brain and spinal cord MRI at week 12, 24, 48 and 96
- Neurophysiological assessment (OCT, VEP, SSEP, MEP) will be performed at week 24, 48 and 96
- Administration of MsQuol54 will be performed at 12, 24, 48, 72 and 96 weeks

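### Section 7.2 states a 5 mg prednisone decrement that the doses in the same sentence contradict; the intended 25-day taper can be inferred, but the number should be removed

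*Combined protocol and SAP*

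**What the plan says.** The taper is set out only in section 7.2 (Immunosuppression), which gives oral prednisone "50 mg tapering of 5 mg every five days as follows dosage: 37,5 mg, 25mg, 12,5 mg and 5 mg". The lead-in in the same section points forward to it: "According to our hematologist guidelines the patients will receive and oral prednisolone as explained below".

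Other places give the start, the length or a cross-reference:

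- 8.3.3, Day -1: "Prednisone (Deltacortene) administration (50 mg", which fixes the start day and first dose.
- 7.12: the exception to the steroid ban is a "course of oral prednisolone at the above mentioned dosage in the first 25 days after hNPCs injection". This ties a length to the dosage in 7.2.
- Note 12 to Table 1: the drug "will be administered only from day -1 till week 4 as explained in the text".
- 8.3.1: "oral corticosteroids will be administered for the first 4 weeks".
- 8.3.5: "and oral prednisone for 4 weeks".

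The drug is called prednisolone in the 7.2 lead-in and in 7.12, and prednisone in the 7.2 order, note 12, 8.3.3 and 8.3.5. I read all of these as one course. Any prednisone row in Table 1 is not in the text available to me, so I draw nothing from it.

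**The concern.** One sentence gives a rule and a list, and they disagree. A reader who follows the rule from 50 mg goes to 45, 40, 35 and so on. A reader who follows the list goes to 37.5, 25, 12.5 and 5.

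The order applies to every treated patient and comes on top of tacrolimus. Section 5.5.2, under infective complications, names the "risk of opportunistic infections and organ toxicity due to combined steroid and tacrolimus treatment" as something to be monitored. A wrong number in that order is worth removing even if most prescribers would read past it.

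**Working it through.** **Inputs.** Start at 50 mg on day -1 (8.3.3). Listed doses after that are 37.5, 25, 12.5 and 5 mg; the stated decrement is 5 mg; the interval is five days (all 7.2). Stated limits are 25 days after injection (7.12) and week 4 or four weeks (note 12, 8.3.1, 8.3.5), taken as day 28. Assumption: every level, including the first at 50 mg, lasts five days. The single i.v. methylprednisolone dose is left out because it is the same under either reading.

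**1. Can the stated decrement be reproduced?** Successive differences of the listed doses:

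- 50 − 37.5 = 12.5
- 37.5 − 25 = 12.5
- 25 − 12.5 = 12.5
- 12.5 − 5 = 7.5

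None is 5 mg. The figure is not reproduced.

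**2. Which reading fits the stated lengths?**

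- List: 5 levels × 5 days = 25 days. From day -1 the last dose falls on day −1 + 24 = 23.
- 5 mg rule run in full (50, 45, …, 5): 10 levels × 5 days = 50 days. The 5 mg level starts on day −1 + 5 × 9 = 44, which is 16 days after day 28, and the last dose falls on day −1 + 49 = 48.

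The list matches the 25 days in 7.12 and lies inside four weeks. The full 5 mg taper fits none of the stated lengths.

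**3. Cumulative dose if the 5 mg rule were applied and cut at a limit.**

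- List: 5 × (50 + 37.5 + 25 + 12.5 + 5) = 650 mg to day 23. With 5 mg held on, 650 + 2 × 5 = 660 mg to day 25 and 650 + 5 × 5 = 675 mg to day 28.
- 5 mg rule: 5 × (50 + 45 + 40 + 35 + 30) = 1000 mg to day 23. Then 1000 + 2 × 25 = 1050 mg to day 25 and 1000 + 5 × 25 = 1125 mg to day 28.

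| Last day | 5 mg rule | List | Ratio | Last dose, 5 mg rule | Last dose, list |
|---|---|---|---|---|---|
| 23 | 1000 mg | 650 mg | 1.54 | 30 mg | 5 mg |
| 25 | 1050 mg | 660 mg | 1.59 | 25 mg | 5 mg |
| 28 | 1125 mg | 675 mg | 1.67 | 25 mg | 5 mg |

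**4. End date if the list governs.** Holding 5 mg to day 25 adds 10 mg (10/650 = 2%); to day 28 it adds 25 mg (25/650 = 4%). Where the extra days go matters more. One more day at the first level adds 50 mg (50/650 = 7.7%), against 5 mg (5/650 = 0.8%) at the last.

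**The case against.** The best defence is that the sentence nearly settles itself. It prints one dose sequence, which can be followed at five-day intervals. The list ends at 5 mg, so the phrase may simply be a slip for a taper *to* 5 mg. Section 7.12 then supports the list, because its 25 days equal five levels of five days and it refers back to the dosage in 7.2. This stands. A reader might infer that the protocol holds two competing dosing orders with nothing to choose between them, and the documents do not support that.

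The second objection is that the 1.5 to 1.7 ratios come from a constructed case. The prescriber would have to ignore the only printed doses, build an unprinted sequence and then stop at 25 or 30 mg. That also stands. The ratios bound a misreading and do not describe an expected exposure.

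Third, 25 days and four weeks may be an exact and a rounded statement of the same course, since 25 doses from day -1 end on day 23. That is plausible, and the dose difference is only 2 to 4%.

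The printed number is still wrong, and no visible text withdraws it. The length limits exclude a full 50-day taper but not a 5 mg taper cut short; only the list excludes that. A dosing order should not need the reader to count back from the section on prohibited therapy.

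**Conclusion.** The point holds, as a minor one. The 5 mg decrement in 7.2 contradicts the doses in its own sentence, and nothing visible restates or corrects it. The probable intent is 50, 37.5, 25, 12.5 and 5 mg for five days each: 25 doses, 650 mg, ending on day 23. This is an inference from the list, the 25 days in 7.12 and the four-week limits. It assumes that the 50 mg level also lasts five days and that the prednisone and prednisolone wording means one course.

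A reader might also infer that patients are likely to be overdosed or that dose escalation is put at risk. The documents do not support either. The trial has one centre, visits are weekly for the first four weeks, and the investigator may cut or stop immunosuppression for toxicity (7.2). Section 7.10 excludes events related to tacrolimus and steroids from the DLT definition. The worst-case misreading is 1.54 to 1.67 times the steroid at the same end date.

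**What to change.** In 7.2, delete the 5 mg decrement and write: *50 mg from day -1, then 37.5, 25, 12.5 and 5 mg, five days at each dose, then stop.*

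Before adopting this, have the sponsor's clinicians confirm the sequence, the length of the 50 mg level and the last dosing day against the haematology guideline that 7.2 relies on. If the course is meant to run past 25 doses, say which level is longer. Then put that one end date in note 12, 7.12, 8.3.1 and 8.3.5; under the wording above it is day 23.

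The cost is protocol wording only. Sample size, visits and escalation rules do not change.
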